8. ADVERSE EVENTS (AA)

8.1. Definition

Adverse event is any unfavorable medical event that occurs in a patient or subject undergoing clinical investigation who is administered a product Pharmaceutical, regardless of whether or not it is considered related to the product pharmacist. Any sign (including alteration of a laboratory parameter), symptom or disease, unfavorable and unintended, that appears associated temporarily with the use of a medicinal product can constitute an event adverse.

Unexpected adverse events are those experiences not described (in nature, severity or frequency) in the technical data sheet of the product.

8.2 Description of adverse events

Previous publications have shown that the interventions proposed in this rehearsal are safe. Our preliminary clinical experiences with autologous MSV and in General MSC have not identified any Adverse Health or Safety Event caused or associated with them.

Possible risks related to sedation combined with necessary local anesthesia for bone marrow aspiration in the MSV donor group are: hypoxemia, arrest respiratory, aspiration pneumonia, hypotension and death. However the probability of a complication of this severity should be considered exceptional.

Possible risks related to donor bone marrow aspiration are:

□ Minimal bleeding from a puncture site; minor complication, only requires a compression bandage.

□ Feeling of nausea and instability in the hours following sedation. By This reason is usually kept in hospital for the next 2 hours to obtaining.

 \Box An allergic reaction to any of the anesthetic drugs used is considered an exceptional complication, with an incidence of less than 1 in 50,000 anesthesia.

 $\hfill\square$ Fever, sometimes a few tenths in the first hours after obtaining.

□ Pain in the puncture sites that is quickly controlled with pain relievers common, paracetamol type, and usually disappears in less than 48 hours. To promote its resolution, it is recommended to take a few days of relative rest.

Interventions carried out during treatment (local injection of mepivacaine or Allogeneic MSV) derived from product infiltration are minor, and attributable to the diagnostic recording technique, namely, the risk associated with the sedation, possibility of infection or bruising, death. However, it is understood that the treatment proposed in this study does not imply risks greater than those of surgery habitual of the contemplated pathology. Rather, it involves avoiding a technique open surgical procedure and the implantation technique is the same as that used in the discography, a widely used and widely used diagnostic technique experience. Sedation and local anesthesia are assumed to maintain very high risk levels. low under conditions of good clinical practice Aside from local pain or swelling, the arm of allogeneic MSV may have theoretically immunological rejection, although, as detailed in another section, MSCs have little or no antigenic power and this type of phenomenon has not been described or in animal experiments (rabbit and pig) or in clinical trials conducted in patients with lupus erythematosus ((Sun et al., 2009; Liang et al., 2010).have obtained similar results with allogeneic mesenchymal cells derived from cord blood (Sun et al., 2010) There are also numerous treated cases of patients with breast cancer (Koc et al., 2000) graft versus host disease (Lazarus et al., 2005), and other autoimmune diseases (Bernardo et al., 2009; Bernardo et al., 2011) without that there have been, so far, adverse effects. Finally, there are 44 declared trials clinicians using allogeneic MSCs in the "clinicaltrials.gov" database for treatment of very varied pathologies, including not only graft-versus-host disease and different autoimmune diseases, but also ischemic strokes, cardiac or peripheral disorders, liver destruction, osteogenesis imperfecta or degeneration of the intervertebral disc (see

http://clinicaltrials.gov/ct2/results?term=mesenchymal+allogenic). On summary, both animal experimentation and use in human clinical trials demonstrates the safety of allogeneic mesenchymal cells, without having reported adverse effects. The collection of Adverse Events must be carried out by the researcher responsible for the trial, describing it according to its duration, intensity, frequency and relationship of causality between the treatment and the adverse event. The researcher should ask indirect questions directed to the patient at each visit of the study. Adverse events can also be reported voluntarily by the patient during or between visits or detected in physical examinations, laboratory tests or in other evaluations. In the Data Collection Notebook (CRD) of the study, the researcher must record in reference to A: A. Duration: refers to the time elapsed since the occurrence of the event until completion.

B. Intensity: it will be defined according to a scale of three gradations:

□ mild: does not interfere with the subject's daily life

□ moderate: interferes but does not impede normal activity.

□ severe: interferes with some important aspect of daily life and can even force to abandon the treatment.

C. The frequency: it will be defined as: punctual, recurring or persistent.

D. The causal relationship: it will be established according to the classification in which the following categories:

□ Not related

- Unlikely
- Possible
- Probable

True

8.3 Record of Adverse Events

Adverse events observed during the clinical trial, either either by the researcher or by the patient himself, they must be recorded in the description of adverse events. This form can be found in the CRD of each participant in the study.

Adverse Events will be recorded from the moment the patient signs informed consent. All of them will be logged, regardless of the relationship of imputed causality.

8.4 Serious Adverse Event (AAG)

8.1.4.1 Definition

A Serious Adverse Event is any unfavorable medical event that any dosage of the product or due to specific study procedures:

□ Produces the death of the patient,

□ Threatens life,

□ Produces permanent or significant disability,

□ It gives rise to hospitalization or prolongation of it, (hospitalizations scheduled prior to patient selection or study procedures, will not be considered AAG).

□ Congenital anomalies and malignant processes.

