6.1.4 Post-treatment regime

The patient is discharged after a 2-hour observation period. Not prescribed Lumbostat corset and walking is allowed for moderate periods. Activity is suspended work for a week. Exercises to tone the muscles are prescribed para-vertebral and abdominal, which begin one month after the intervention. Medication analgesic is adapted to the needs of each patient and use should be avoided as far as possible of anti-inflammatories. Long-term follow-up will consist of clinical visits and monitoring Radiographic and MRI as specified in point 7.2 ("Schedule").

6.1.5. Possible complications derived from the proposed therapy.

The complications are the same as in the discography, and they occur very rarely. The most common complaint is exacerbation of pain for 1-2 weeks, which usually resolved by analgesia and muscle relaxants for a period short. The most serious complication is discitis, the incidence of which is less than 0.1% (Osti et al., 1990). Other complications described, although much less frequently, are transient headache, nausea, meningitis, epidural abscess, arachnoiditis, bruising intrathecal, retroperitoneal hematoma, cauda equina syndrome and acute disc herniation. Isolated cases of urticaria are not considered in this trial, as they are attributable to contrast medium. Initial fears about possible side effects of the Long-term discography regarding disc viability have not been confirmed. In a study with up to 20 years of clinical follow-up, no radiographic evidence was found of progressive disc degeneration after discography (Flanagan & Chung, 1986). The possible risk of complications derived from the use of allogeneic cells has been discussed in detail above. Suffice now to summarize that, according to the literature, the application of Allogeneic MSCs, both locally and systemically, have been shown to be safe both in the context of clinical trials and studies in animal models. Either way, will monitor skin and mucosal reactivity to watch for a possible immune reaction.

6.1.6. Methodology for obtaining bone marrow from donors.

This procedure will be applied to donors, generally included in the Eudra trial. CT2009-017405-11 (MSV_Artro) that we are carrying out or in compassionate cases authorized

by the AEMPS, and that follow the same protocol and that provide their cells left over for this test (see section 5.3).

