11.2.1 Main objectives, main variables

- Evaluate the feasibility and safety of the use of allogeneic MSV injected into the disc space for the treatment of lumbar degenerative disc disease and pain and the disability it causes.

The variables that will be used to evaluate safety will be the AAG number related to study medication and the percentage of patients who presented a related AGS. -Evaluate the analgesic-anti-inflammatory efficacy determined by the variation of the Low back pain assessment questionnaire scores (VAS), disability (Oswestry) and health and quality of life (SF12) at 3, 6 and 12 months.

- Evaluate regenerative efficacy using quantitative MRI imaging criteria determined by the appearance of improvements in disc dehydration at 6 and 12 months.

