7. DESCRIPCIÓN DE LA REACCIÓN DESENLACE													

I. INFORMACION SOBRE LA REACCIÓN ADVERSA

- < LA VIDA DEL PACIENTE HA ESTADO EN PELIGRO
- < HOSPITALIZACIÓN
- < PROLONGACIÓN HOSPITALIZACIÓN
- < INCAPACIDAD PERMANENTE O SIGNIFICATIVA
- < RA CLINICAMENTE RELEVANTE
- < PERSISTENCIA DE LA REACCIÓN ADVERSA
- < RECUPERACIÓN

SIS			DIO		INICIO			19. DURACI	
20. ¿REMITIÓ LA REACCIÓN AL SUSPENDER LA			RE	a. ¿REMITIÓ ACCIÓN AL DUCIR LA		REAC	EAPAR CIÓN AL IISTRAF	-	LA NUEVO LA

II. INFORMACIÓN DEL MEDICAMENTO EN INVESTIGACIÓN

JII. MEDICAMENTOS CONCOMITANTES E HISTORIA CLÍNICA 23 DA LOS IMPORTANTES DE LA HISTORIA CLINICA (ej. diagnósticos, alergias, embarazos, etc.)

IV. INFORMATION ON THE SPONSOR

24a. NOMBRE Y DIRECCION DEL PROMOTOR		24b. NOMBRE Y	DIRECCION DEL INVESTIGADOR		
24c. CODIGO DE LABORATORIO (Nº AEM)	25a. TIPO DE INFORME <inicial <seguimiento< td="">24c. TECNICO DEL PROMOTOR QUE INFORMA NOMBRE: TELEFONO: FIRMA:	</seguimiento<></inicial 		24c. TECNICO DEL PROMOTOR QUE INFORMA NOMBRE: TELEFONO: FIRMA:		
24e. FECHA DEL INFORME	24f. FECHA DE I	ENTRADA AEM	25b. SE ADJUNTA INFORME COMPLEMENTARIO		

GENERAL INSTRUCTIONS

1. This form will only be used to report suspected adverse reactions (AR) serious and unexpected occurrences with investigational drugs. It is considered medicine under investigation, both the specifically investigated product and the control.

2. Suspected fatal or life-threatening adverse reactions (those that are not having mediated an immediate therapeutic intervention would have meant the death of the patient)

They will communicate within a maximum period of 7 calendar days; if not all the information is available, this it can be completed within an additional 8 days. Other suspected adverse reactions serious and unexpected will be communicated within a maximum period of 15 days.

3. When the available space is insufficient, an additional information sheet will be added, correctly identified with the name of the promoter and the number assigned to the notification. In this Additional information may include the evaluation of causality carried out by the technician that informs.

SPECIFIC INSTRUCTIONS

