1. The protocol code is the one assigned by the promoter to identify the assay. The number of the promoter notification is the one that the promoter uses for its file. When it comes to information from the tracking number will be used or, if it is modified, the number of the initial notification. The "Notification No." space that appears shaded will be left unfilled.

2. The age will be set in years, months, weeks or days as appropriate, but always indicating it. the age is not precisely known, it must refer, at least, to the age group to which it belongs (p. eg: infant, child, adolescent, adult, elderly).

3. The adverse reaction will be described in full, indicating the end date of the itself and including the results of complementary examinations or laboratory tests that are considered of interest. This notification may be accompanied by as many reports as deemed convenient for the proper interpretation of the clinical picture suspected of being a reaction adverse.

4. The categories are not mutually exclusive. Assistance in an Emergency Service of a Hospital less than 24 hours, hospitalization will not be considered.

5. Investigational drugs will be identified if possible by their generic name (DOE or DCI), indicating when the commercial name is available, or failing that, by the name proposed or laboratory code for the product.

6. In the event that the administration is not daily, an attempt will be made to describe it with one of the following possibilities: cyclical, weekly, monthly, yearly or number of times it has been used (putting in in this case the dose of each dose, not the total).

7. The pathological process of the patient to whom the product is intended shall be recorded in research, or "healthy volunteer" in case of such.

8. The duration of treatment until the beginning of the adverse reaction will be stated. 9. It will be explicitly stated if concomitant drugs have not been taken. In the case of considering suspicious one or some of the concomitant drugs will be marked with an asterisk (e.g.: * AMOXICILLIN). Medications used to treat the adverse reaction will be excluded.

Measurement of leg pain (sciatic pain) in daily activities.

Assess the sciatic pain that you present today when carrying out activities of your daily life in the last 4 weeks, putting a vertical mark on the horizontal line that we present. The left side represents the absence of pain and the right, a pain unbearable.

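### The serious-event definition in 8.1.4.1 lacks the clinically relevant criterion printed on the Annex IV form, so some related complications can fall outside the main safety variables

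*Combined protocol and SAP*

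**What the plan says.** Section 8.4 (8.1.4.1) defines a serious adverse event (AAG) with the lead-in "A Serious Adverse Event is any unfavorable medical event that any dosage of the product or due to specific study procedures" and a closed list. The list holds death, threat to life, "Produces permanent or significant disability", "It gives rise to hospitalization or prolongation of it" and, as its last item, "Congenital anomalies and malignant processes".

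Section 8.1.4.2 tells the investigator to send each AAG on the Annex IV form. Next to the boxes for threat to life, hospitalisation, its prolongation and disability, that form prints "RA CLINICAMENTE RELEVANTE" (clinically relevant adverse reaction). Specific instruction 4 of the annex adds: "Assistance in an Emergency Service of a Hospital less than 24 hours, hospitalization will not be considered".

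Section 11.2.1 ties the safety result to this definition: "The variables that will be used to evaluate safety will be the AAG number related to study medication", together with the percentage of patients who had a related one. (The text prints AGS at that point; I read it as AAG.)

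All other adverse events (AA) are logged whatever their causality (8.3). They are reported as lists and as frequencies and percentages, separately from AAGs (11.3.6).

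**The concern.** The definition and the form do not carry the same criteria. An investigator holding both cannot tell whether a clinically relevant event that meets no item in 8.1.4.1 should be classed as an AAG. Taken literally, 8.1.4.1 says no, while the form offers a box for it.

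This matters because safety is the main objective (sections 1 and 3.1) and both variables named for it in 11.2.1 count only AAGs. The setting makes the gap plausible. The injection is an outpatient procedure with discharge after two hours (6.1.4), and short emergency care does not count as admission. Sections 2.6.3 and 6.1.5 name discitis and acute disc herniation among the possible complications, and say that skin and mucosal reactivity will be watched for an immune reaction. Some presentations of these could meet none of the listed criteria.

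**Working it through.** The plan gives no event rate, power or derived figure for safety, and 11.1 fixes 12 patients per arm by phase. There is therefore no stated figure to reproduce. The check compares the texts and then works out the consequence at n = 12.

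**Step 1. Criteria side by side**

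| Criterion | 8.1.4.1 | Annex IV boxes |
|---|---|---|
| Threat to life | yes | yes |
| Hospitalisation or prolongation | yes | yes |
| Permanent or significant disability | yes | yes |
| Clinically relevant reaction | **no** | **yes** |
| Persistence, recovery (outcomes) | no | yes |

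The form mixes seriousness and outcome items. The clinically relevant box is not an outcome and stands with the seriousness items. The form's table is broken in the available text, so I draw nothing from boxes that do not appear in it.

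**Step 2. Which events fall in the gap**

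An event is missing from the 11.2.1 variables because of this gap only if all of these hold:

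- it is judged related to study medication;
- it is not fatal, does not threaten life and causes no permanent or significant disability;
- it needs no admission, where emergency care under 24 hours does not count as one;
- it is neither a congenital anomaly nor a malignancy;
- it is nevertheless clinically relevant.

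Such an event would appear only under AA in 11.3.6.

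**Step 3. Size for one such event in the MSV arm, with no other AAG**

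Exact (Clopper-Pearson) 95% intervals:

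- Not counted, 0/12: upper limit 1 − 0.025^(1/12) = 0.2646, so 0% (0 to 26.5%).
- Counted, 1/12 = 8.3%: lower limit 1 − 0.975^(1/12) = 0.0021; the upper limit solves (1 − p)^12 + 12p(1 − p)^11 = 0.025, giving p = 0.3848. The interval is 0.2 to 38.5%.
- Two such events counted, 2/12 = 16.7%: 2.1 to 48.4%.

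**Step 4. How likely such an event is**

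For discitis, 6.1.5 gives only a ceiling: "The most serious complication is discitis, the incidence of which is less than 0.1" per cent. Taking that as a rate per disc (my assumption, as the unit is not stated), the chance of at least one case is at most 1 − 0.999^12 = 1.2% over 12 discs. It is at most 1 − 0.999^24 = 2.4% over 24, if all 12 patients had two discs treated. Discitis alone is thus an unlikely route, and the practical weight lies more with immune and other local reactions.

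The documents give no rate for those reactions. As an assumption, let p be the true rate of clinically relevant related events per patient and let half of them meet 8.1.4.1:

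| p | At least one occurs, 1 − (1 − p)^12 | At least one counted, 1 − (1 − p/2)^12 |
|---|---|---|
| 5% | 46% | 26% |
| 10% | 72% | 46% |
| 20% | 93% | 72% |

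**The case against.** The strongest case against the point has four parts.

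1. **Care setting does not decide seriousness.** A reader might infer that discitis or disc herniation treated without admission can never be an AAG. The text does not support that: threat to life and significant disability count wherever the patient is treated. The documents also do not say that these complications would be managed as outpatient cases. Only events that meet none of the listed criteria are affected.

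2. **The events are neither hidden nor necessarily slow to be reported.** Section 3.1 includes recording adverse effects in the main objective, 8.3 logs all of them, and 11.3.6 lists them by relationship and severity. In 24 patients a listed discitis would be seen. A reader might also infer that such events escape immediate notification. That does not follow, because 8.1.4.2 also covers unexpected events, and 8.1 judges expectedness by nature, severity or frequency against the product's technical data sheet. The product dossier in Annex I lists no complications.

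3. **Relatedness is a separate hurdle.** Section 11.2.1 counts events related to study medication, while 8.2 attributes the infiltration risks to the technique. A discitis judged to come from the puncture could stay out of the count even if classed as an AAG.

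4. **Annex IV is a form and not a definition.** Its boxes mix outcomes with seriousness, and its first general instruction limits it to suspected reactions that are serious and unexpected.

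All four stand as limits on the point. They do not remove it, because 8.1.4.2 adopts this form for every AAG, the form carries a criterion that the definition lacks, and the 11.2.1 variables rest on the definition. The form's own limit to serious and unexpected reactions is a further mismatch with 8.1.4.2.

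**Conclusion.** The mismatch is real and touches the main safety result, but it is narrow. A related, clinically relevant event that does not threaten life, causes no significant disability and is managed without admission is left out of both 11.2.1 variables and appears only in the AA listings and frequencies. One such event makes the difference between 0/12 (95% CI 0 to 26.5%) and 1/12, 8.3% (0.2 to 38.5%). That assumes the event is judged related to study medication and that no other AAG occurs in the arm.

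The plan names no stopping rule, test or sample size that depends on the AAG count. The harm is therefore to how the headline safety figure reads; the record itself is kept. This is a reconciliation to make, of moderate weight.

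A reader might go further and want every complication named in 6.1.5, and any suspected immune reaction, to count as serious automatically. The mismatch does not call for that. Skin and mucosal reactivity is actively watched, so such a rule would turn a mild, passing skin reaction into a serious event.

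**What to change.** Add one item to the list in 8.1.4.1: *any other event that the investigator judges clinically relevant, as on the Annex IV form*. Align 8.1.4.2 and the first general instruction of Annex IV in the same amendment, so that it is clear whether the form serves every AAG or only serious and unexpected suspected reactions. The definition, the form and the 11.2.1 variables then rest on one set of criteria.

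The cost is a line or two of text, a few more AAG reports and possibly a less favourable safety figure. The new item also rests on the investigator's judgement, so the count becomes somewhat less mechanical. Because 8.3 already logs all adverse events from consent, no new data collection is needed.

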8.1.4.2 Notification of Serious Adverse Events (AAG)

The investigator is responsible for the immediate reporting of adverse events. serious or unexpected. The investigator must notify any AAG to the CRO (FTH) in the within one working day from the moment the investigator learns of the existence of the serious or unexpected adverse event, regardless of the causal relationship.

The minimum information that an initial report of a serious adverse event must collect (It can be notified by phone, fax or via email) is:

□ name of the researcher,

□ protocol code,

□ study drug,

□ patient identification number,

description of the event,

□ start date,

severity criteria and

causality of the event

The investigator should send the trial monitor within 24 hours of the When you become aware of an AAG, the Notification of AAGs form (Annex IV) completed, signed, dated and with all the information available at the time.

In the event that the AAG or unexpected has caused the death of the subject or placed in

danger to his life, the investigator will contact the trial monitor and send the form Serious Adverse Event Notification Form completed and signed and dated on the within 24 hours from the moment the researcher becomes aware of the same.

The CRO (FTH) will act on behalf of the Promoter to notify the AEMPS, the CEIC that is applicable and the competent bodies of the applicable Autonomous Communities, the suspicions of serious and unexpected adverse reactions that may be related to the investigational drug. Likewise, all the participating researchers.

Unexpected causal related AAGs will not be notified to the competent authorities with other procedures of routine clinical practice in the treatment of these pathologies, particularly those of surgical procedures. Expected serious adverse events, non-serious adverse events and those that are considered unrelated to the treatments under study will be included in a tabulated in the annual or final report of the clinical trial.

